7.3 Initiation of a New Cycle

See section 7.2 Dose Modifications. Treatment with study drugs will be repeated every 21 days. Initiation of a new cycle requires that all toxicity considered related to treatment with study drugs must have resolved to grade ≤ 1 , to the patient's baseline values, or to a level considered acceptable by the treating physician after discussion with the principal investigator. If criteria for treatment are not met, initiation of the next cycle of treatment may be delayed for up to 2 weeks. If treatment criteria are not met after a 14-day delay, study treatment will be discontinued.

In certain circumstances and with agreement from the principal investigator, after Cycle 1, consideration may be given to allowing an additional rest week in subsequent cycles thus lengthening the cycle to 4 weeks to support the patient's need for time off between cycles, *e.g.*, during holidays.

7.4 Resumption of Treatment Within a Cycle

See section 7.2 Dose Modifications. MLN4924 (pevonedistat) doses must be separated by at least one full calendar day. In each cycle, a maximum of 3 doses of MLN4924 (pevonedistat) and 5 doses of belinostat should not be exceeded.

7.5 Dose Re-escalation

If a dose reduction is incurred for a \leq grade 3 toxicity; and that toxicity is resolved ; and that toxicity has not recurred at the reduced dose; then, with approval of the principal investigator (or designee), the dose may be re-escalated (to no higher than the enrollment dose) in the next cycle.

7.6 Dose Modifications Requiring Discontinuation of Protocol Therapy

See section 6.7.

8. PHARMACEUTICAL INFORMATION

A list of the AEs and potential risks associated with the investigational or commercial agents administered in this study can be found in Section 10.1.

8.1 CTEP IND Agent(s)

8.1.1 MLN4924 (Pevonedistat-HCL) (NSC # 793435)

Chemical Name: ((1S,2S,4R)-4-{(1S)-2,3-dihydro-1H-inden-1-ylamino]-7H-pyrrolo[2,3-d]pyrimidin-7-yl}-2-hydroxycyclopentyl) methyl sulfamate hydrochloride

Classification: NEDD8-activating enzyme (NAE) inhibitor

Other Names: TAK924/MLN4924; MLN4924-003 (hydrochloride salt); MLN4924-001 (free base);

NCI Protocol #: 10246
Version Date: 02/16/2022

ML00644807; ML644507

CAS Registry Number: 905579-51-3 (free base); 1160295-21-5 (hydrochloride salt)

Molecular Formula: C₂₁H₂₆ClN₅O₄S

M.W.: 443.52 (free base); 479.98 (hydrochloride salt)

Mode of Action: MLN4924 (pevonedistat) is an inhibitor of neural precursor cell expressed development down-regulated 8 (NEDD8)-activating enzyme or NAE. NAE is essential in the NEDD8-conjugation pathway to control the activity of a subset of multiprotein complexes that transfer NEDD8 molecules to protein substrates by E3 ligases. NAE inhibitors stop the degradations of a subset of proteins that regulated by the proteasomes.

Description: White to off-white solid with an assay value of 96.0% to 103.0% (w/w) on an anhydrous basis. Acid dissociation constants of pKa1 = 5.16 and = 8.81.

How Supplied: Takeda supplies and PMB distributes MLN4924 (Pevonedistat HCl) formulated as 10 mg/mL Concentrate for Solution for Infusion. Each single-use vial contains either 50 mg (5 mL) or 44 mg (4.4 mL) free base equivalent containing the following excipients: citric acid (anhydrous), trisodium citrate dihydrate, and Betadex Sulfobutyl Ether Sodium (Captisol®) at pH 3.3. The sterile solution is packaged in USP Type I glass vials with rubber stoppers (latex free), aluminum seals with plastic caps.

The current supply is 50 mg (5 mL) with 0.3 mL overfill volume. At a future date, the 44 mg (4.4 mL) vial configuration will replace the 50 mg (5 mL) vial configuration. The 44 mg (4.4 mL) vial contains 0.3 mL overfill volume.

Preparation: Before use, bring MLN4924 (Pevonedistat HCl) vials to ambient room temperature (15°-30°C/59°-86°F) for 15 minutes. Do not use a water bath to warm up the vials. Return vials to 2°-8°C (36°-46°F) storage if not used within 6 hours.

- Use a 250 mL **prefilled** 5% Dextrose (D5W) or 0.9% Normal Saline (NS) IV bag:
 - Remove excess volume from 250 mL D5W or NS prefilled IV bag
 - Add the calculated dose (mL) of pevonedistat
 - Final volume (250 mL) = drug + D5W or NS
 - Do not shake; gently mix the IV solution by inverting the IV bag several times
 - Inspect the IV solution to ensure it is clear and free of visible particles
- Alternatively, a 250 mL **empty IV bag can be used:**
 - Add the required volume of D5W or NS into the empty IV bag
 - Add the calculated dose (mL) of pevonedistat o Final volume (250 mL) = Drug + D5W or NS
 - Do not shake; gently mix the IV solution by inverting the IV bag several times
 - Inspect the IV solution to ensure it is clear and free of visible particles

Materials: PVC or Polyolefin bags; non-DEHP IV bag is preferred but not required

Storage: Store MLN4924 (Pevonedistat HCl) refrigerated at 2°-8°C (36°-46°F) in its original

carton to protect from light.

If a storage temperature excursion is identified, promptly return MLN4924 (Pevonedistat HCl) to 2°-8°C (36°-46°F) and quarantine the supplies. Provide a detailed report of the excursion (including documentation of temperature monitoring and duration of the excursion) to [REDACTED] determination of suitability.

Stability: Stability studies are ongoing.

- Once MLN4924 (Pevonedistat) prepared IV solution is complete, the prepared IV solution must be used within 6 hours when stored at ambient room temperature. Discard the IV bag if it cannot be used within 6 hours.
- Alternatively, the prepared IV solution is stable up to 18 hours when stored at 2°-8°C (36°-46°F), after which the IV bag can be used within 3 hours upon removal from 2°-8°C storage. The prepared IV solution must be brought up to ambient room temperature before administering to patient. If cannot used within 3 hours, the prepared IV solution must be discarded.

Route of Administration: Intravenous

Method of Administration: Infuse over 60 minutes (+/- 10 minutes) through peripheral IV-line, midline or central venous access. The IV infusion can be slowed or stopped and restarted for any associated infusion-related reactions. The total time from the IV preparation to end of IV infusion must not exceed 6 hours. Infusion line can be flushed with 5% Dextrose in Water or 0.9% Normal Saline immediately after IV administration is complete. Protecting IV bag from light during IV infusion is not required.

Potential Drug Interactions: In vitro, pevonedistat is metabolized mainly by hepatic CYP3A4/5 and to some extent by CYP2D6 (3%). CYP1A1 and 2J2 appear to be involved in extrahepatic metabolism, which may explain the lack of drug-drug interaction with CYP3A4/5 inhibitors. This was demonstrated in an in vivo PK study where a moderate CYP3A inhibitor (*e.g.*, fluconazole) and a strong CYP3A4 inhibitor (*e.g.*, itraconazole, which is also a strong P-gp inhibitor) did not result in interactions when administered with pevonedistat. Therefore, drugs that are CYP3A/P-gp inhibitors can be used in patients receiving MLN4924 (pevonedistat).

In vitro, pevonedistat is not an inhibitor of CYP1A2, 2C9, 2C19, 2D6, or 3A4/5 (IC₅₀ > 100 μM and K_i >50 μM) but is a weak inhibitor of CYP2B6 and 2C8 (IC₅₀ = 97.6 and 23.1 μM, respectively). Pevonedistat causes concentration-dependent decreases in CYP1A2, 2B6, and 3A4/5 mRNA expression and/or activities, but is not expected to affect the PK of CYP1A2, 2B6 or 3A4/5 substrates.

Pevonedistat is a substrate of P-gp and BCRP, and a weak inhibitor of P-gp, OATP and BCRP-mediated transport. Pevonedistat is unlikely to affect the PK of known P-gp, BCRP or OATP substrates.

Because the metabolic and excretion pathways of pevonedistat remain to be fully characterized in

humans, the risk of drug-drug interactions between pevonedistat and concomitantly administered drugs are currently informed by available nonclinical and clinical data. As a general precaution, patients receiving concomitant medications, particularly those with narrow therapeutic indices, should be carefully monitored.

8.1.2 Belinostat (NSC # 726630)

Chemical Name: (E)-N-hydroxy-3-(3-(N-phenylsulfamoyl)phenyl)acrylamide

Other Names: PXD101; Beleodaq®

Classification: HDAC inhibitor

CAS Registry Number: 414864-00-9; 866323-14-0

Molecular Formula: C₁₅H₁₄N₂O₄S **M.W.:** 318.35

Approximate Solubility: Water 0.14 mg/mL; ethanol >200 mg/mL;

polyethylene glycol 400 ~ 1.5 mg/mL; 1,2-propanediol ~ 0.2 mg/mL

Mode of Action: Histone deacetylases (HDACs) are a family of enzymes that regulate chromatin remodeling and gene transcription via the dynamic process of acetylation and deacetylation of core histones. Belinostat is a novel and potent HDAC inhibitor of the hydroxamate class. It alters acetylation levels of histone and non-histone proteins, thus influencing chromatin accessibility and ultimately gene transcription.

How Supplied: Spectrum Pharmaceuticals supplies and the PMB, CTEP, DCTD distributes belinostat in single-use 30 mL clear glass vials with coated stoppers and aluminum crimp seals with “flip-off” caps containing 500 mg belinostat for injection. The sterile yellow lyophilized product also contains 1000 mg arginine, European Pharmacopoeia/ US Pharmacopoeia (Ph. Eur/USP).

Preparation: Reconstitute the lyophilized product with 9 mL sterile water for injection to yield a final belinostat concentration of 50 mg/mL. Before IV administration, further dilute in 250 mL 0.9 % sodium chloride injection.

Storage: Store intact vials of belinostat at controlled room temperature (20-25°C; 68-77°F); brief excursions permitted (15-30°C; 59-86°F). Leave intact vials of belinostat in the secondary packaging until use.

If a storage temperature excursion is identified, promptly return belinostat to controlled room temperature and quarantine the supplies. Provide a detailed report of the excursion (including documentation of temperature monitoring and duration of the excursion) to [REDACTED] for determination of suitability.

Stability: Shelf life stability studies of intact vials of belinostat are on-going; once the lyophilized product is reconstituted, the vial solution is stable for up to 12 hours at ambient temperature (15-25°C).

Once further diluted in 250 mL of 0.9% sodium chloride, belinostat may be stored at ambient temperature (15-25°C) for up to 36 hours, including the infusion time.

Route and Method of Administration: Infuse belinostat IV over 30 minutes through a 0.22

micron in-line filter.

Potential Drug Interactions: Belinostat is primarily metabolized by hepatic UGT1A1, and to a lesser extent by CYP2A6, CYP2C9 and CYP3A4 enzymes. Avoid concomitant use of strong inhibitors of UGT1A1. Use caution when co-administering agents which may compete for UGT1A1 metabolism, such as irinotecan. Patients with known UGT1A1 genetic polymorphisms, such as UGT1A1*28, can have reduced UGT1A1 activity and may be at risk for increased belinostat exposure. If subjects with UGT1A1 genetic polymorphisms are not excluded from study participation, reduced doses are warranted.

In vitro studies have shown belinostat and its metabolites are weak to moderate inhibitors of CYP2C8 and moderate to strong inhibitors of CYP2C9; however, studies did not demonstrate effects when co-administered with warfarin. Avoid CYP2C8 and CYP2C9 substrates during belinostat treatment unless deemed medically necessary.

Belinostat is likely a P-gp substrate but is unlikely to inhibit P-gp.

Avoid concomitant medications that may cause Torsade de Pointes.

Availability: Belinostat is an investigational agent supplied to investigators by the DCTD, NCI. Belinostat is provided to the NCI under a Collaborative Agreement between the Pharmaceutical Collaborator and the DCTD, NCI (see Section 13).

8.1.3 Agent Ordering and Agent Accountability

8.1.3.1 NCI-supplied agents

NCI-supplied agents may be requested by eligible participating investigators (or their authorized designee) at each participating institution. The CTEP-assigned protocol number must be used for ordering all CTEP-supplied investigational agents. The eligible participating investigators at each participating institution must be registered with CTEP, DCTD through an annual submission of FDA Form 1572 (Statement of Investigator), NCI Biosketch, Agent Shipment Form, and Financial Disclosure Form (FDF). If there are several participating investigators at one institution, CTEP-supplied investigational agents for the study should be ordered under the name of one lead participating investigator at that institution.

Confirmation of patient enrollment onto study is required for initial supply.

Submit agent requests through the PMB Online Agent Order Processing (OAOP) application. Access to OAOP requires the establishment of a CTEP IAM account and the maintenance of an “active” account status, a “current” password, and active person registration status. For questions about drug orders, transfers, returns, or accountability, call or email PMB any time. Refer to the PMB’s website for specific policies and guidelines related to agent management.

8.1.3.2 Agent Inventory Records

The investigator, or a responsible party designated by the investigator, must maintain a careful record of the receipt, dispensing and final disposition of all agents received from the PMB using the appropriate NCI Investigational Agent (Drug) Accountability Record (DARF) available on the CTEP forms page. Store and maintain separate NCI Investigational Agent Accountability Records for each agent, strength, formulation and ordering investigator on this protocol.

8.1.4 Investigator Brochure Availability

The current versions of the IBs for the agents will be accessible to site investigators and research staff through the PMB OAOP application. Access to OAOP requires the establishment of a CTEP IAM account and the maintenance of an “active” account status, a “current” password and active person registration status. Questions about IB access may be directed to the PMB IB Coordinator via email.

9. STATISTICAL CONSIDERATIONS

9.1 Study Design/Endpoints

This study will be a phase 1 trial of MLN4924 (pevonedistat) and belinostat in relapsed/refractory acute myeloid leukemia or myelodysplastic syndrome employing a “3+3” dose escalation strategy applied to 4 dose levels, with provision for 1 level of dose reduction. Additional patients will be enrolled at the MTD until a total of 12 patients have been treated at the MTD.

Primary endpoint

- RP2D for the combination of MLN4924 (pevonedistat) and belinostat in the study population.

Secondary endpoints

- AEs using NCI CTCAE v5.0.

- Treatment responses classified according to International Working Group (IWG) and European Leukemia Net (ELN) criteria for response assessment in AML and MDS. Duration of response defined as the time from documentation of tumor response to disease progression or death, whichever occurs first. Time to response defined as the time from registration to the time of documentation of tumor response.
- [REDACTED]
- MLN4924 (pevonedistat) and belinostat plasma concentrations measured at baseline (pre-treatment) and at defined time points in Cycle 1.
- Candidate biomarker levels in bone marrow and/or blood samples pre- and 24-hr post-treatment with the first doses of study drugs (e.g., p-Wee1, p-cdc2 and γ -H2A.X).

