NCT03772925
Phase 1 Study of MLN4924 (Pevonedistat) and Belinostat in Relapsed/Refractory
Acute Myeloid
Leukemia or Myelodysplastic Syndrome
2/16/2022

[REDACTED]

[REDACTED]

[REDACTED]

[REDACTED]	[REDACTED]	[REDACTED]
[REDACTED]	[REDACTED]	[REDACTED]

NCI Protocol #: 10246
Version Date: 02/16/2022

NCI Protocol #: 10246

ClinicalTrials.gov Identifier: NCT03772925

TITLE: A Phase 1 Study of MLN4924 (pevonedistat) and Belinostat in Relapsed/Refractory Acute Myeloid Leukemia or Myelodysplastic Syndrome

[REDACTED]

Principal Investigator:

[name], DO

[REDACTED]

Participating Organizations

[REDACTED]

Statistician:

[REDACTED]

Study Coordinator:

VCU Massey Cancer Center
Investigator-Initiated Trials (IIT) Program

[REDACTED]

[REDACTED]

[REDACTED]

NCI-Supplied Agent(s): MLN4924 (pevonedistat) (NSC 793435), Belinostat (NSC 726630)

IND #: 142135

NCI Protocol #: 10246
Version Date: 02/16/2022

IND Sponsor: DCTD, NCI

[Redacted]

[Redacted]

SCHEMA

This will be a two-part phase 1 dose-escalation and dose-expansion study of MLN4924 (pevonedistat) in combination with belinostat. Part A will be a 3+3 dose-escalation study of the combination to assess its safety and tolerability and identify a maximum tolerated dose (MTD)/recommended phase 2 dose (RP2D). Part B of the study will be a dose expansion study of 12 patients treated at the MTD/RP2D.

Dose Escalation Schedule				
Dose Level	Belinostat		MLN4924 (pevonedistat)	
	Dose (mg/m²/day)	Administration and Schedule	Dose (mg/m²/day)	Administration and Schedule
-1	800	Intravenously over 30 minutes once daily on Days 1-5 of each 21-day cycle	15	Intravenously over 60 minutes once daily on Days 1, 3, & 5 of each 21-day cycle**
1*	800		20	
2	800		25	
3	800		37	
4	1000		37	
5	1000		50	
6***	1000		59	

* Starting dose level

** When both drugs are given on the same day (Days 1, 3, 5), start the MLN4924 (pevonedistat) infusion within 60 mins after the completion of belinostat infusion.

*** The 59 mg/m² level will not begin until the NCI/CTEP, Principal Investigator and Takeda have closely examined the toxicity, PK and clinical data from the 50 mg/m² cohort. Takeda must give written approval for the 59 mg/m² to begin.

TABLE OF CONTENTS

SCHEMA.....	3
1.1 Primary Objectives.....	6
1.2 Secondary Objectives.....	6
2. BACKGROUND	6
2.1 Study Diseases	6
2.2 CTEP IND Agents	7
2.3 Rationale	13
2.4 Correlative Studies Background	14
2.5 Pharmacokinetic Studies Background	16
3. PATIENT SELECTION	16

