6. TREATMENT PLAN

6.1 Agent Administration

This will be a two-part phase 1 dose-escalation and exploratory dose-expansion study of MLN4924 (pevonedistat) in combination with belinostat. Part A will consist of a 3+3 dose-escalation phase of the combination to assess its safety and tolerability and identify an MTD/tentative RP2D. After the MTD has been established, Part B of the study will involve an exploratory-dose expansion study of 12 additional patients who will be enrolled at the tentative RP2D to gain further insights into the safety of the regimen. MLN4929 (pevonedistat) and belinostat dose rounding is allowed per institutional guidelines.

Treatment will be administered on an outpatient basis. Cycles are to be repeated every 21 days. Reported adverse events and potential risks are described in Section 10. Appropriate dose modifications are described in Section 7. Other than hydroxyurea during the first 5 days of study treatment, no investigational or commercial agents or therapies other than those described below may be administered with the intent to treat the patient's malignancy.

Dose Escalation Schedule				
Dose Level	Belinostat		MLN4924 (pevonedistat)	
	Dose (mg/m²/day)	Administration and Schedule	Dose (mg/m²/day)	Administration and Schedule
-1	800	Intravenously over 30 minutes once daily on Days 1-5 of each 21-day cycle	15	Intravenously over 60 minutes once daily on Days 1, 3, & 5 of each 21-day cycle**
1*	800		20	
2	800		25	
3	800		37	
4	1000		37	
5	1000		50	
6***	1000		59	

* Starting dose level

** When both drugs are given on the same day (Days 1, 3, 5), start the MLN4924 (pevonedistat) infusion within 60 mins after the completion of belinostat infusion.

*** The 59 mg/m² level will not begin until the NCI/CTEP, Principal Investigator and Takeda have closely examined the toxicity, PK and clinical data from the 50 mg/m² cohort. Takeda must give written approval for the 59 mg/m² to begin.

Regimen Description				
Agent	Premedication; Precautions	Dose And Route	Schedule	Cycle Length
Belinostat	See Section 6.4	In 250 mL 0.9% NaCl IV over 30 (± 5 min)*** Dose per assigned dose level.	Days 1-5 (week 1)	21 days (3 weeks)
MLN4924 (pevonedistat)	See Section 6.4	In 250 mL D5W or 0.9% NS IV over 60 min (± 10 min)* Infusion to start within 60 minutes after belinostat infusion ends. Dose per assigned dose level.	Days 1, 3, & 5 (week 1)**	

IV = Intravenously; D5W = dextrose 5% in water; NS = normal saline.

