6.3 Dose Escalation

Dose escalation will proceed within each cohort according to the following scheme.

Number of Patients with DLT at a Given Dose Level	Escalation Decision Rule
0 out of 3	Enroll 3 patients at the next dose level.
≥ 2	Dose escalation will be stopped. This dose level will be declared the maximally administered dose (highest dose administered). Three additional patients will be entered at the next lowest dose level if only 3 patients were treated previously at that dose.
1 out of 3	
Enroll at least 3 more patients at this dose level.
 
If 0 of these 3 patients experience a DLT, proceed to the next dose level (unless MTD has already been exceeded at that dose level, in which case, the current dose level is the MTD).
 
If 1 or more of this group experience DLT, then dose escalation is stopped, and this dose is declared the maximally administered dose. Three additional patients will be enrolled at the next lowest dose level if only 3 patients were treated previously at that dose

≤ 1 out of 6 at highest dose level below the maximally administered dose	This is the MTD and is generally the RP2D. At least 6 patients must be entered at the RP2D.

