6.4 Dose Expansion Cohorts

The RP2D may be equal to, but may not exceed, the MTD. A RP2D below the MTD may be considered given the overall tolerability of the treatment including the frequency of AEs that do not qualify as DLTs and the frequency of dose modifications.

Once the RP2D is reached, an additional 12 patients will be treated at this dose. For the expansion cohort, patients will continue to be monitored for occurrence of DLT. If 2 of the first 5

patients or ≥ 2 of 12 patients experience DLT, the principal investigator will discuss with all study investigators and with CTEP whether further addition of patients is needed to re-assess the RP2D. Monitoring of all safety and toxicity data is done by the Principal Investigator and the Corresponding Organization on a real-time basis as data are entered into Medidata Rave using the Web Reporting Module.

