9.2 Sample Size/Accrual Rate

With this classical 3+3 design, there is no statistical testing, rather a variety of dose-escalation strategies will be employed to target a DLT rate of <33%. Applying this design to the 5 dose levels (-1, 1, 2, 3 and 4), starting with dose level 1 (as indicated in Table 1 in Section 6), the total number of patients evaluable for DLT ranges from 3 to 24. Assuming an average of 4 or 5 patients per dose level (some may require 3, other 6), approximately 18 patients can be anticipated. Accounting for approximately 20% of patients subsequently found to not be evaluable for DLT, enrollment of 23 patients is expected in Part A (3+3 phase), with a maximum of 30.

During the expansion cohort for dose/schedule refinement (Iasonos and O’Quigley, 2016), an additional 15 patients (factoring in the 20% DLT inevaluability as well) will be treated at MTD, leading to a maximum sample size of 45, with a likely size between 35-42

Stopping rule: The 3+3 is a straightforward algorithmic design, where development of DLTs in more than 1 of 6 subjects in a specific dose cohort suggests that the MTD has been exceeded, and further dose escalation is not pursued. So here, the stopping rule is to repeat until MTD is achieved, or the trial is stopped.

PLANNED ENROLLMENT REPORT

Racial Categories	Ethnic Categories				Total
	Not Hispanic or Latino		Hispanic or Latino		
	Female	Male	Female	Male	
American Indian/ Alaska Native	0	0	0	0	0
Asian	0	0	0	0	0
Native Hawaiian or Other Pacific Islander	0	0	0	0	0
Black or African American	7	6	0	0	13

Racial Categories	Ethnic Categories				Total
	Not Hispanic or Latino		Hispanic or Latino		
	Female	Male	Female	Male	
White	16	14	1	1	32
More Than One Race	0	0	0	0	0
Total	23	20	1	1	45

PHS 398 / PHS 2590 (Rev. 08/12 Approved Through 8/31/2015)

OMB No. 0925-0001/0002

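### Section 9.1 caps the dose at a cumulative 12 patients, leaving about 6 new patients in the expansion, where 6.1 and 6.4 plan 12 and 9.2 sizes the trial for 12

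*Combined protocol and SAP*

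**What the plan says.** Five places in the combined protocol and SAP describe the size of the expansion.

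- **Schema:** "Part B of the study will be a dose expansion study of 12 patients treated at the MTD/RP2D".
- **Section 6.1:** "12 additional patients who will be enrolled at the tentative RP2D".
- **Section 6.4:** "Once the RP2D is reached, an additional 12 patients will be treated at this dose". The DLT check for this cohort is written as "If 2 of the first 5" "patients or ≥ 2 of 12 patients experience DLT", and meeting it prompts a discussion with the investigators and CTEP.
- **Section 9.1:** "Additional patients will be enrolled at the MTD until a total of 12 patients have been treated at the MTD".
- **Section 9.2:** 15 further patients at the MTD, a figure said to include 20% DLT inevaluability. For the escalation part, "enrollment of 23 patients is expected in Part A (3+3 phase), with a maximum of 30". The resulting totals are a maximum of 45 and a likely size of 35-42, and the planned enrollment table also sums to 45.

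On how many patients are already at the dose when expansion starts, Section 6.3 identifies the MTD from at most 1 DLT in 6 and adds: "At least 6 patients must be entered at the RP2D".

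**The concern.** The sentence in 9.1 counts everyone treated at the dose, including those treated there during escalation. The other sections count new patients. With 6 escalation patients already at the dose, a total of 12 is half the expansion that 6.1 and 6.4 describe.

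Section 9.1 is the statistical statement of the design, so a statistician or monitor would look there to see when accrual to Part B is complete. If it were followed, the expansion would close about 6 patients early, and patients 7 to 12 of the DLT check in 6.4 would never be observed. Part B is meant to add safety information, and it would yield about half of what was planned.

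**Working it through.** **Inputs from the documents.** Section 9.2: about 18 expected and 24 maximum DLT-evaluable patients in Part A; 20% inevaluable; 23 and 30 enrolled in Part A; 15 more in the expansion; 45 maximum and 35-42 likely. Sections 6.1 and 6.4: 12 additional patients. Section 6.3: 6 patients at the MTD. Section 9.1: cumulative total of 12 treated.

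**Step 1: reproduce 9.2.** Enrolled = evaluable / (1 − 0.20).

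- Part A expected: 18 / 0.8 = 22.5, rounded up to 23. Matches.
- Part A maximum: 24 / 0.8 = 30. Matches.
- Expansion: 12 / 0.8 = 15. Matches if the base is 12 new patients.
- Maximum total: 30 + 15 = 45. Matches the text and the enrollment table.
- Expected total: 23 + 15 = 38, inside 35-42.

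That 15 is 12 inflated is an inference, since 9.2 does not state the base. It uses the same inflation that reproduces both Part A figures.

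**Step 2: apply 9.1 as written, with the RP2D equal to the MTD.**

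- New patients: 12 − 6 = 6.
- Because 9.1 counts patients treated, inevaluable Part A patients at that dose also use up places. At 20% inevaluability, 6 evaluable patients imply 6 / 0.8 = 7.5 treated, say 7 or 8, which leaves 4 or 5 new.
- Totals with 6 new patients: 23 + 6 = 29 expected and 30 + 6 = 36 maximum. Since 6 may be too many, read these as no more than about 29 and 36.

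Part A figures are taken from 9.2 as given. Its count of dose levels differs from the dose table, but that is a separate matter and is not needed here.

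| | 9.1 read literally | 12 additional | Stated in 9.2 |
|---|---|---|---|
| New patients | about 6 or fewer | 12 (15 enrolled) | 15 enrolled |
| Expected total | no more than about 29 | 38 | 35-42 |
| Maximum total | no more than about 36 | 45 | 45 |

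**Step 3: effect on the DLT check in 6.4.** The true DLT rate p = 20% is an assumption; the documents give no such figure. P(at least 2 of n) = 1 − (1 − p)^n − n·p·(1 − p)^(n−1).

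- n = 6: 1 − 0.2621 − 0.3932 = 0.345 (34%).
- n = 12: 1 − 0.0687 − 0.2062 = 0.725 (73%).

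The gap depends on the rate. At 10% the chances are 11% and 34%; at 30% they are 58% and 91%.

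**Step 4: does 15 enrolled deliver 12 evaluable?** With each patient evaluable with probability 0.8, P(at least 12 of 15) = 0.648, about 65%. Sections 6.2 and 9.3.1 require inevaluable patients to be replaced, so in roughly one case in three replacement would go past 15.

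**The case against.** The strongest reply is that 9.1 is one loosely worded sentence. The Schema, 6.1, 6.4, 9.2 and the enrollment table all fit 12 new patients, Part B will be run from Section 6, and expansion decisions need the Principal Investigator's sign-off. Early closure on the strength of 9.1 is therefore unlikely. That limits the severity. It does not remove the contradiction: the wording of 9.1 covers escalation patients at the dose, and it sits in the section that defines the design.

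A second reply is that 6 is not a strict limit. Section 6.3 does not say that all 6 patients must enter during escalation, and its table gives no instruction for 0 of 3 DLTs at the top level. If only 3 had been treated there, 9.1 would leave 12 − 3 = 9 new patients. This is fair, and is why the figure is given as about 6. Nine is still short of 12.

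A reader might infer more than the documents support:

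- *That there are three competing targets: 12 in total, 12 additional and 15 additional.* The 15 is best read as 12 allowing for inevaluability. Section 9.1 alone is out of line.
- *That the safety check is disabled.* With 6 new patients, the check on the first 5 is unchanged, and 2 DLTs among 6 already meet the count. The trigger starts a discussion; it does not stop the trial. A higher chance of triggering is also not pure gain: at a true rate of 10%, some of those triggers would be false alarms.

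**Conclusion.** Section 9.1 is wrong as written and should be corrected. Its cumulative total of 12 leaves about 6 new patients, or fewer, against the 12 planned in 6.1 and 6.4 and used to size the trial in 9.2. The contradiction is certain from the text. The figure of 6 rests on the RP2D being the MTD and on 6 patients having been treated there in Part A. The totals of 29 and 36 are upper values that also rest on the Part A figures in 9.2. The DLT probabilities are illustrations at assumed rates.

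This is an inconsistent sample size in the statistical section, not a missing safeguard.

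A related inconsistency should be settled in the same edit. Sections 9.1 and 9.2 place the expansion at the MTD, while 6.1 and 6.4 place it at the RP2D. Section 6.4 allows the RP2D to lie below the MTD, so the two labels need not mean the same dose level.

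**What to change.** - **Section 9.1:** replace the cumulative wording with: *12 additional patients will be treated in Part B (about 15 enrolled, allowing for 20% DLT inevaluability, as in 9.2)*.
- **Section 9.2:** if inevaluable Part B patients are to be replaced beyond 15, describe 45 as a planned total and not as a strict maximum. If 45 is meant as a limit, say that replacement ends there.
- **Sections 6.1, 6.4, 9.1 and 9.2:** reconcile whether the expansion dose is called the MTD or the RP2D.

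The cost is one sentence in 9.1, possibly a few words in 9.2, and a consistent label. No analysis changes. If replacement beyond 15 is allowed, enrollment could exceed 45, and the sponsor should accept that openly. The edit does not settle whether the Part A total in 9.2 is right.
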